- Decreased SpO₂ reading during treatment with difference of >6% compared to a non injured extremity or deterioration of clinical signs
- Deterioration of any of the 5 “P” signs: Pain, Paralysis, Pulselessness, Pallor, Paraesthesia

Since in such cases the eschar removal procedure will not be completed as planned, such patients (if any) will still be part of the full analysis set (FAS, see Definition in Appendix 13.1.1) and any missing data usually collected during eschar removal (e.g. time to end of eschar removal, etc.) will be handled as missing data according to the protocol.

In case of 3 consecutive cases where there is a need to disrupt the dressing and perform a surgical escharotomy, enrollment will be halted and a DSMB shall be convened to:

- assess the severity of the phenomenon in a closed session
- Recommend on appropriate corrective measures, as applicable to prevent such reoccurrences

As discussed above, increased interstitial/compartment pressure is a common medical condition in circumferential deep burns and its detection and resolution is part of daily standard of care. The only difference in the treatment of the patients in the study is during the eschar removal stage as dictated by randomization.

Coagulopathy during or within 24 hours of eschar removal

It is evident that during the first 48 hours post injury there is deterioration in coagulation parameters in burn patients [22]. In addition, some burn patients are treated with

anticoagulants after admission (in some burn centers all patients are treated with anticoagulants). Due to these facts, any stopping rule concerning coagulopathy after topical debriding agent application must take these factors into consideration.

Enrollment will be halted and a DSMB will convene if 3 subjects develop the following signs which have been defined as life threatening coagulopathy in trauma patients:

INR>2 or a PTT>2 times the normal range [23], in cases where the patient is not receiving anticoagulants that can explain the coagulopathy.

A DSMB shall be convened to assess in a closed session the following:

- The relationship between coagulopathy and the treatment arm
- The severity of the phenomenon
- Recommend on appropriate corrective measures, as applicable to prevent such reoccurrences

DSMB investigation will consider patients' medical history, including any anticoagulants given to the patient prior to start of treatment.

Post treatment diagnosed infection (until complete wound closure)

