7.2. Trial schedule

The healing and care of the burn wound may be divided into the three distinctive phases:

1. Eschar removal treatment phase (until complete eschar removal)
2. Wound management (until complete wound closure)
3. Scar modulation and maturation

These phases are common to the care of all wounds and are well defined in acute wounds such as burns.

In this study, these phases and their treatment strategy are equal for all arms, NexoBrid, SOC, and Gel Vehicle, following the ABA white paper recommendations [24].

The total duration of the study treatment and follow up period of each participating subject is expected to be 25 months: following the Eschar removal procedure, each subject will be followed up weekly (Weeks 1, 2, 3 and 4 etc.) until complete wound closure is achieved and 2 weeks later for wound closure confirmation, for each of the subject's TWs. Long-term follow-up visits will be performed at 1, 3, 6, 12, 18 and 24 months post last wound closure confirmation visit (for details see Table 1).

Table 1: Treatment flow chart - all arms³

If applicable
 * Weekly FU assessments will be performed every 7± 2 days from start of treatment until complete wound closure. Long-term FU will be performed 1,3,6,12,18 and 24 M after last wound closure confirmation.
 **First treatment session will include any procedure for eschar removal: the NexoBrid®/Gel Vehicle/Surgical or non-surgical procedure, as per randomization arm
 ** Procedure can be either surgical or non-surgical. A whole period of continuous dressing changes (from first coverage application to last coverage application) is considered as one non-surgical procedure, assessments should not be repeated for each dressing change; Pre procedures assessments refer only to surgical procedures. Post procedures assessments refer to any surgical procedures and for non-surgical procedure only if it is the last procedure

Parameter	Screening tests	Baseline within 1 h Pre First treatment session - All arms	Topical arms (NexoBrid or Gel Vehicle): (refer to first and second application). S=Soaking, R=Removal	SOC procedures** (including additional procedures in the topical arms)	Daily assessments	Management & Re-admissions ⁴ - surgical procedures assessment	Wound	HD or premature discontinuation visit	Weekly FU*	Long-Term FU (1, 3, 6,12,18 & 24 months)*
Inform Consent signing	X									
Medical history	X									
Burn History ⁵	X									
ConMeds & AEs	X	X	X	X	X	X	X	X	X	X

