Parameter	Screening tests	Baseline within 1 h Pre First treatment session - All arms	Topical arms (NexoBrid or Gel Vehicle): (refer to first and second application). S=Soaking, R=Removal	SOC procedures** (including additional procedures in the topical arms)	Daily assessments	Wound Management & Re-admissions ⁴ - surgical procedures assessment	HD or premature discontinuation visit	Weekly FU*	Long-Term FU (1, 3, 6, 12, 18 & 24 months)*
PK (for a subset of 32 NexoBrid Pts)		X	During: 0.5, 2, 4h from start of first application		12,24,48, 72h				
Immunogenicity assessment (NexoBrid patients only)		X						weeks 4,8 ¹⁰	Long-term FU: 6, 24
Local lab PTT & INR		X	4 h post R - first application only	4 h post- first treatment only	24,48h				
Circumferential extremity wounds monitoring ¹¹		X	during and post R (4 hours from start)	1h pre & post					
Eschar Removal treatment			X	X	Start and end date , type of primary dressing		Type of primary dressing& frequency		
Coverage									

¹⁰ In case that 8 weekly visit is not performed, this assessment should be taken on the relevant weekly/first visit as close as possible to 8 weeks.

¹¹ The Extremities At Risk (EAR) burns prone to develop BICS will be identified at screening and excluded. Monitoring for the development of EAR in circumferential extremity wounds at the above specified timelines will be done. During each topical application (NexoBrid or gel Vehicle), clinical assessment and SpO₂ monitoring will be done continuously. If such assessment is not practical, direct pressure will be measured every 2 hours from start of eschar removal. Direct pressure will be measured before and after each eschar removal procedure and additional surgical procedures

Parameter	Screening tests	Baseline within 1 h Pre First treatment session - All arms	Topical arms (NexoBrid or Gel Vehicle); (refer to first and second application). S=Soaking, R=Removal arms	SOC procedures** (including additional procedures in the topical arms)	Daily assessments	Wound Management & Re-admissions ⁴ - surgical procedures assessment	HD or premature discontinuation visit	Weekly FU*	Long-Term FU (1, 3, 6, 12, 18 & 24 months)*
Wound closure confirmation ¹²								X	Long-term FU: 1, 3
Cosmesis, Function and Quality Of Life ¹³								X	
Scar-modulating procedures and scar					#			#	
Blood transfusion (units & volume)	#	#	#	#	#	#	#	#	
Histological biopsy	#	#	#	#	#	#	#	#	

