Serum chemistry, hematology and urinalysis testing will be performed at a central laboratory during the eschar removal phase. Any additional procedures during the wound management phase require hematology tests, as described in the protocol, and will be performed using Central lab. Pregnancy testing, HbA1c, leukocyte count (at Screening, in addition to central lab hematology), wound cultures, blood cultures, PTT/INR and biopsies will be performed locally on-site.

The following tests are performed in special laboratories: Pharmacokinetics test, Immunogenicity evaluation and evaluation of QT prolongation (using multiple ECG tests).

Serum Chemistry:

Urea, Creatinine, Glucose, Total Bilirubin, Cholesterol, Triglycerides, Uric Acid, Total Protein, Albumin, Globulin, Calcium (Ca++), Phosphorous, Sodium (Na+), Potassium (K+), Chloride (Cl-), Alkaline Phosphatase, SGOT (ASAT), SGPT (ALAT), LDH.

Hematology:

Hemoglobin, Hematocrit, RBC, MCV, MCH, MCHC, Platelets, Leukocyte count (WBC) with differential count (absolute numbers).

HbA_{1c} will be assessed at a local lab at Screening for diabetic patients as captured during the medical history.

PTT and INR will be tested at a local lab pre treatment and 4 hours after start of eschar removal.

Pregnancy Testing:

A serum pregnancy (β HCG) will be performed at a local lab for women of child bearing potential.

Urinalysis:

pH, Ketone, Specific gravity, Protein, Glucose, Bilirubin, Microscopic examination.

Qualitative Wound Culture:

Test burn wound for microbial flora (swab).

Blood Culture:

Test blood for microbial flora.

Diagnosis of Invasive Burn Wound Infection is based on Quantitative (Histological) Wound Culture Biopsy:

Infection should be assessed clinically by symptoms and signs that include local burn wound signs purulent drainage, erythema, warmth, exudation, odor, pain, and systemic signs that may or may not be related to the burn wound, such as fever, and leukocytosis as well as wound size and time to wound healing. Histological Biopsy may be performed to rule out suspicion of a clinical invasive burn wound infection (please refer to Appendix 8- Biopsy & Histologic Assessment Method) [26].

Clinical Invasive Burn Wound Infection will be defined when an Invasive Burn Wound Infection is diagnosed by quantitative bacterial count of $>10^5$ organisms per gram of tissue and histological signs of bacterial invasion of healthy tissues will define a positive invasive burn

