For each patient in the topical arms a binary (yes/no) variable is indicating whether the patient developed a burn-induced compartment syndrome (BICS) during the eschar removal procedure is given in the data.

Incidence of QT prolongation

Incidence of QT prolongation will be analyzed separately. The analysis and all needed transformations are described in a separate document.

Rates of hospital readmission

For each hospital readmission, a binary (yes/no) variable will be computed indicating whether this readmission was planned or not. A readmission will be considered as being planned when the reason for readmission was indicated as “planned wound management” or “scar modulation” in the eCRF. Readmissions for which the reason was given as “AE” in the eCRF are considered as being unplanned. Hospital readmission for which the reason is given as “other” will be reviewed by blinded personnel of the sponsor in order to decide whether they are to be classified as planned or unplanned.

For each patient a binary (yes/no) variable will be computed indicating whether this patient had a hospital readmission or not. Furthermore, a variable giving the number of planned hospital readmissions and a variable giving the number of unplanned readmissions will be computed for each patient.

Relative and absolute frequencies of hospital readmission will be calculated per treatment arm.

Change in PTT/INR

Change in PTT/INR will be computed as change from pre Eschar Removal procedure to 4h ± 15 min post first application (Topical arms) respectively to 4h post first SOC treatment (SOC arm) for each patient. Additionally, change from baseline PTT/INR will be computed for the first and second daily assessment post treatment (24h & 48h after start of debridement).

The proportion of patients with a change to > upper limit of normal range PTT/INR (patients with normal PTT/INR at baseline and PTT/INR > upper limit of normal range at the respective time point) will be computed per treatment arm and time point of measurement (4h post treatment, 24 h, 48h). Reference count is the number of patients with normal PTT/INR values at baseline. For the classification of normal and abnormal PTT/INR values, the reference limits of the local labs will be used.

Change in blood glucose

Change in blood glucose will be computed as change in blood glucose value from pre first topical procedure to 4h post first topical procedure (4h after removal of topical) and from

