11.1.4.16. INR/PTT change

Change in INR/PTT will be evaluated at 4h post first treatment as well as on the first and second daily assessment post treatment separately. This is a binary (yes/no) variable indicating whether the patient experienced a change of INR/PTT to > normal range (reference limits of the local laboratories). Rates of patients with this event will be analyzed by displaying counts and percentages by treatment group (see Table 5) in each time point separately (4h post, 24h and 48h). Reference count is the number of patients with normal PTT/INR values at

baseline. For the classification of normal and abnormal PTT/INR values, the reference limits of the local labs will be used. The proportion of patients with change of INR/PTT to > normal range will be compared between treatment groups using a chi square test (or Fisher's exact test in case of small estimated cell counts).

INR/PTT values will be classified as normal, abnormal (NCS) and abnormal (CS) based in the eCRF. These will be analyzed by displaying counts and percentages by treatment group (see Table 5) for each time point separately (4h post, 24h and 48h).

11.1.4.17. *Blood glucose change*

This is a binary (yes/no) variable indicating whether the patient experienced a change of blood glucose to > upper limit of normal range. Rates of patients with this event will be analyzed by displaying counts and percentages by treatment group (see Table 5) per eschar removal procedure. Furthermore, bar plots will be displayed. The proportion of patients with change of blood glucose to > upper limit of normal range will be compared between treatment groups using a chi square test (or Fisher's exact test in case of small estimated cell counts).

Furthermore, the change in blood glucose from baseline to 4h post treatment per patient will be analyzed descriptively with number of units, number of missing values, mean, standard deviation, min, max, median and quartiles as shown in Table 4 and compared between groups with a one way analysis of variance. A graphical representation of the data will be done using histograms.

11.1.5. *Exploratory Analyses*

11.1.5.1. *% wound area surgically excised for eschar removal*

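### The tested INR/PTT rate does not separate severe from mild elevations and omits patients abnormal at baseline, and its 4 h time point is not comparable between the topical and SOC arms

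*SAP*

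**What the plan says.** **Stopping rule (SAP 7.1.4.1).** Under the subheading "Coagulopathy during or within 24 hours of eschar removal", enrolment halts and the DSMB convenes if three subjects show "INR>2 or a PTT>2 times the normal range [23], in cases where the patient is not receiving anticoagulants that can explain the coagulopathy". The rule covers the two topical arms. The same text notes that coagulation worsens in the first 48 hours after a burn and that some centres anticoagulate every patient.

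**Endpoint and derivation (7.3.3.6, 10.3.4.4).** Section 7.3.3.6 lists two things: the change in INR/PTT, and the incidence of a change to above the upper limit. Section 10.3.4.4 derives a numeric change to 4 h, 24 h and 48 h, then the proportion crossing the limit among patients normal at baseline.

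**Analysis (11.1.4.16).** "This is a binary (yes/no) variable indicating whether the patient experienced a change of INR/PTT to > normal range". This is compared between treatment groups at each time point by chi-square or Fisher's exact test. A second, untested table shows normal, abnormal not clinically significant and abnormal clinically significant, by arm and time point.

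**Sampling time.** For the topical arms, Table 1 has "4 h post R - first application only". For SOC, 10.3.4.4 takes the change "respectively to 4h post first SOC treatment (SOC arm) for each patient". The Table 1 footnotes count a whole run of dressing changes as one non-surgical procedure and add: "Post procedures assessments refer to any surgical procedures and for non-surgical procedure only if it is the last procedure". Section 7.3.3.5 says something different: "PTT and INR will be tested at a local lab pre treatment and 4 hours after start of eschar removal". The 24 h and 48 h samples are counted from start of debridement.

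**The concern.** Coagulopathy is one of three risks for which the plan would halt enrolment, so a reader of the safety results will want to know how many patients in each arm reached the severe level. The tested rate does not say. It scores a value slightly over the limit and an INR above 2 alike, and a patient who starts above the limit and rises past 2 is not in the denominator at all.

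The second issue is comparability at the first time point. If the SOC patients who contribute a 4 h value are determined by the type of care given after randomisation, and some are sampled days later than topical patients, the 4 h test between arms does not compare randomised groups at a common time.

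**Working it through.** The SAP states no figure for the INR/PTT analysis, so there is none to reproduce. The check sets the sections side by side and adds up the sampling times.

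**1. Does another planned analysis report the threshold?**
- PTT and INR are local-laboratory tests (7.3.3.5). The central-laboratory categories and summaries (10.3.6, 11.1.4.10) therefore do not cover them.
- The clinical-significance table in 11.1.4.16 has no stated baseline restriction, but its categories are not linked to INR>2, PTT>2 times normal or anticoagulant use.
- The opening of 10.3 asks for mean, SD, minimum, maximum and quartiles by arm for every continuous variable. That would cover the numeric change, but 11.1.4.16 does not take it up. Section 11 sends variables it does not mention to the case-wise listing, which 13.4 places outside the statistical report.
- Section 11.1.4.17, on glucose, analyses both the shift and the numeric change.

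No planned table names the threshold.

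**2. What can the tested rate hide?** Illustration with assumed counts: suppose 60 of 75 patients per arm are normal at baseline (20% abnormal) and 20 of 60 cross the limit in each arm. Fisher's exact p = 1.0, however many of the crossings in one arm exceed INR 2. The SAP gives no baseline-abnormal rate. At 10% to 40%, the denominator is 75 × 0.90 = 67.5 down to 75 × 0.60 = 45.

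**3. Hours from start of eschar removal to the 4 h sample.**

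| Group | Calculation | Hours |
|---|---|---|
| Topical (Table 1, 10.3.4.4) | 4 h application (7.1.2) + 4 h | about 8 |
| SOC, surgery first | length of surgery + 4 h | same day |
| SOC, dressings only | dressing period + 4 h | 244 to 340 if 10 to 14 days |
| SOC, dressings then surgery | no post-procedure sample under the Table 1 footnote | apparently none |
| Any arm, if 7.3.3.5 is taken literally | 4 h from start | 4 |

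The third row uses 10 × 24 + 4 = 244 and 14 × 24 + 4 = 340. The 10 to 14 days comes from the background in 2.1, not from an expected dressing period for this trial.

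**4. How many SOC patients?** Section 9.2 gives an SOC excision rate of 0.62 in the previous trial and 0.60 for planning; section 9.3.1 plans 75 SOC patients.
- No excision: 75 × 0.38 = 28.5, or 75 × 0.40 = 30.
- Excision: 75 × 0.62 = 46.5, or 75 × 0.60 = 45.

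The SAP does not split the second group into surgery-first and dressings-first. The share of SOC patients with a same-day sample is therefore anywhere from 0% to 62%.

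**5. What would a threshold table show?** With 75 per arm, two-sided Fisher p-values are 0.24 for 3 vs 0, 0.058 for 5 vs 0 and 0.028 for 6 vs 0. Its value would be mainly descriptive.

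**The case against.** The strongest reply has four parts.

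**The halt does not use this table.** This is correct. The stopping rule works on individual topical-arm cases, judged by the DSMB in closed session with anticoagulants considered. A reader might infer that 11.1.4.16 weakens the halt; nothing in the SAP supports that.

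**Severe cases are not invisible.** This also stands in part. The clinical-significance table covers all patients, adverse events are listed, and the general rule in 10.3 would give a minimum and maximum of the change. A reader might conclude that the plan is unable to show severe coagulopathy or counts nothing but limit crossings. That goes too far: what is missing is a report against the plan's own threshold.

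**The SOC timing is inferred.** A general footnote is being applied to a row with its own timing, and 10.3.4.4 speaks of each patient, so the first SOC treatment might mean the first dressing. Some ambiguity remains. But the footnotes treat the dressing period as one procedure with assessments not repeated at each change. The amendment summary in 13.5 (version 9 to 11, lines 24 and 26) points the same way: no PTT/INR after surgery that is not the first procedure, and post-assessments after dressings only when they end eschar removal. It would also be wrong to read every SOC sample as late or absent, since surgery-first patients are sampled the same day.

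**Little rests on it.** INR/PTT lies outside the testing hierarchy, the test is worded as between treatment groups rather than as a dedicated NexoBrid–SOC contrast, and the 24 h and 48 h comparisons are aligned. This limits the consequence to the reading of one safety variable, chiefly at one of three time points.

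**Conclusion.** The point holds within limits. The only tested INR/PTT variable does not distinguish mild elevation from the level the plan treats as life-threatening, and it leaves out patients abnormal at baseline. The listed numeric change has no analysis in 11.1.4.16. Sections 7.3.3.5, 10.3.4.4 and Table 1 disagree on when the early sample is taken.

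At 4 h only, the arms are not comparable under the Table 1 rules: about 8 h from start in the topical arms, against the end of the dressing period for roughly 28 to 30 of 75 SOC patients and apparently no sample for those who go from dressings to surgery. These figures assume that the plan's excision rates hold and that the footnote governs this row. The 244 to 340 h range further assumes dressing periods as long as the background text suggests. How far the 4 h comparison would be distorted cannot be established, because the SAP gives no split by first procedure.

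**What to change.** Changes to the SAP:

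1. In 11.1.4.16, base the NexoBrid–SOC comparison on the 24 h and 48 h samples. Show SOC 4 h values descriptively, by type of first procedure, with hours since start.
2. Add a descriptive table of counts by arm and time point of INR>2 or PTT>2 times normal, whatever the baseline, with and without anticoagulants that could explain the value.
3. State in 11.1.4.16 that the numeric change from 10.3.4.4 is summarised by arm, as 11.1.4.17 does for glucose.
4. Reconcile the sampling time in 7.3.3.5 with Table 1 and 10.3.4.4, and state what the first SOC treatment means when care begins with a dressing period.

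The cost is SAP wording and two further tables from data already collected. The 4 h NexoBrid–SOC p-value is given up.

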11.1.5.4. Incidence of surgically harvested donor site wounds

This is a counting variable, giving the number of donor site wounds per patient. Rates of patients with different numbers of donor site wounds will be analyzed by displaying counts and percentages by treatment group (see Table 5). Furthermore, bar plots will be displayed (see Figure 2). The number of donor site wounds will be compared between treatment groups using a chi square test (or Fisher's exact test in case of small estimated cell counts).

11.1.5.5. % area of surgically harvested donor site wounds

The % wound area of surgically harvested donor site wounds per patient (computed as in section 10.3.5.11) will be analyzed descriptively with number of units, number of missing values, mean, standard deviation, min, max, median and quartiles as shown in Table 4 and compared between groups with a one way analysis of variance. A graphical representation of the data will be done using histograms.

